5.5.3 Pure Tone Air Conduction Threshold/Bone Conduction Testing

Pure-tone air conduction threshold testing both at baseline and post-treatment (11-15 days after the last day of study drug/placebo administration) will be conducted utilizing the modified Hughson-Westlake procedure. Pure-tone air-conduction testing will be conducted at .5, 1, 2, 3, 4, 6, 8 kHz. Bone conduction testing will be conducted at .5, 1, 2, 3, 4 kHz if the pure tone air-conduction threshold at that frequency is greater than or equal to 15 dB HL. All testing will be conducted using standard Army test procedures using Interacoustic 629 clinical audiometers meeting all Defense Occupational Environmental Health

Readiness System – Hearing Conservation (DOEHRS-HC) and American National Standards Institute (ANSI) criteria. All testing will be conducted in a single -walled sound booth with doors closed, meeting ANSI specifications. Test equipment, test environment, procedures, and personnel will meet all relevant DOEHRs-HC, ASHA, AAA, and ANSI standards and guidelines.

Pure-tone threshold testing will be conducted using the modified Hughson Westlake procedure as follows: Initial descent towards threshold is accomplished in 10-dB steps. Beginning with the first non-response, level is increased by 5-dB for each non-response, and decreased by 10-dB after each correct detection response. Threshold is defined as the lowest level at which two responses are obtained out of three presentations on an ascending run.

Threshold shifts will also be evaluated using DoD significant change criteria and ASHA early detection criteria (1994). Significant noise-induced threshold shifts (STS) in either ear are defined by the DOEHRs-HC as an increase of 10 dB or greater change (decrease in hearing) for the average of 2, 3 AND 4 kHz in either ear. A significant negative STS (improved hearing) is defined as a decrease of 10 dB or greater change (improvement in hearing) for the average of 2, 3 AND 4 kHz in either ear. An early warning shift STS (decrease in hearing) is defined as a 15 dB or greater change at 1, 2, 3 OR 4 kHz in either ear. Subjects with an STS will undergo a final tympanogram screen to rule out middle ear pathology as a cause of the hearing loss. If they pass the tympanogram screen in both ears, they will be referred for a diagnostic audiologic follow-up exam. If they do not pass the tympanogram screen they will be referred for otologic check and then diagnostic audiological assessment.

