Experimental design consists of within-subjects serial testing in which baseline standard frequency (.5, 1, 2, 3, 4, 6, and 8 kHz) audiograms are initially acquired. By comparing similar measures obtained at the end of the study period to the relevant pre-exposure measure, reliable noise-induced changes in pure-tone hearing threshold can be identified. Thus, subjects will serve as their own control for identifying hearing change, relative to their baseline evaluation.

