On days of pure tone air conduction threshold testing, data will be stored for each ear of every subject in the computerized audiometer and will be exported to a centralized Microsoft Access database. These data will also be imported into an Excel spreadsheet for storage and input into a statistical package for offline data analysis. The identifiers in the computer databases will consist solely of the subject identification number (PIN).

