10.0 STATISTICAL CONSIDERATIONS

10.1 Sample Size Justification

Based upon the results of the 2004 study at the Marine Corps Recruit Depot (MCRD), it is estimated that the rate of significant threshold shift (STS) will be approximately 38% for the control (placebo) group. A power analysis incorporating a 95% confidence level ($\alpha = 0.05$), 80% power, a 1:1 ratio (placebo to D-methionine), and a detectable difference in threshold shift rates of 30% yields a required sample size of 252 subjects for each of the two arms (placebo and D-methionine) of the study. Thus a total of 504 subjects need to complete the study. Assuming an attrition rate of 20% in each arm over the course of the study, a total of 600 subjects will need to be enrolled.

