10.2 Primary Efficacy Analysis

Two groups are planned in the randomized prospective design: the D-met and the placebo groups. The primary objectives, and their associated analyses, for this study are as follows:

1. To determine if there is a significant difference between the D-methionine and placebo treated groups in the average severity of documented side effects where severity is defined as the frequency of side effect multiplied by the intensity of the side effect. Repeated measures analysis of variance (ANOVA) will be utilized to determine significance.
2. To determine if there is a significantly reduced change in threshold hearing in each ear, adjusting for handedness, for the D-methionine group as compared to the placebo group at the tested audiometric frequencies. The tested audiometric frequencies will be 0.5, 1, 2, 3, 4, 6 and 8 kHz. Multi-way (2 groups x 7 frequencies) analysis of variance (ANOVA) with interaction effects and correction for multiple comparisons (Newman-Keuls) will be utilized to determine significance. Determination for early detection will be according to the American Speech-Language Hearing Association (ASHA, 1994) criteria of: 1) greater than or equal to a 20 dB change at any frequency, 2) greater than or equal to a 10 dB change at any 2 adjacent frequencies, or 3) loss of response at 3 consecutive frequencies where responses were obtained at baseline. To be considered significant ototoxicity, these changes must replicate within 24 hours (may be immediate) with no indication of middle ear abnormality. Subjects serve as their own controls for audiometric change, which is computed relative to baseline measures.
3. To determine if there is a significantly lower rate of STS (in either ear) for the D-methionine group as compared to the placebo group where STS is defined according to DOEHRSHC criteria as an increase of 10 dB or greater change (decrease in hearing) for the average of 2, 3 AND 4 kHz in

either ear. A significant negative STS (improved hearing) is defined as a decrease of 10 dB or greater change for the average of 2, 3 AND 4 kHz in either ear. An early warning shift STS (decrease in hearing) is defined as a 15 dB or greater change at 1, 2, 3 OR 4 kHz in either ear. Fisher's exact test will be utilized to determine statistical significance.

Secondary objective of the study is as follows:

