1. To determine if there is a significant difference in reported level of tinnitus between the D-methionine and the placebo groups where the level (loudness) of tinnitus will be scored on an eleven point scale with a value of 0 associated with very quiet and a value of 10 associated with very loud and on an eleven point scale where the degree of annoyance secondary to the tinnitus will also be scored on an eleven point scale with a value of zero indicating that it is not bothersome and a value of 10 indicating that it is unbearable. Repeated measures analysis of variance (ANOVA) will be utilized to determine significance.

The 95% confidence intervals will be estimated for all D-methionine vs. placebo differences.

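### The threshold-change ANOVA names no subject or repeated-measures term; fitted as written, its overall group test is anti-conservative if changes are positively correlated across frequencies

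*Combined protocol and SAP*

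**What the plan says.** Section 4.2.1 measures the primary efficacy endpoint in two ways: absolute change in pure-tone threshold, and frequency of significant threshold shift (STS). For absolute change, objective 2 in Section 10.2 prescribes "Multi-way (2 groups x 7 frequencies) analysis of variance (ANOVA) with interaction effects" and "correction for multiple comparisons (Newman-Keuls) will be utilized to determine significance". It names no subject effect, error term or covariance structure.

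For side effects (objective 1) and for tinnitus (secondary objective), the same section does name the method: "Repeated measures analysis of variance (ANOVA) will be utilized to determine significance". It ends with "The 95% confidence intervals will be estimated for all D-methionine vs. placebo differences".

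On the data, Section 5.5.3 says "Pure-tone air-conduction testing will be conducted at .5, 1, 2, 3, 4, 6, 8 kHz", and Section 9.3 says "data will be stored for each ear of every subject in the computerized audiometer". Section 5.5.3 also says "Experimental design consists of within-subjects serial testing in which baseline standard frequency", and objective 2 computes each change against the subject's own baseline. The Synopsis and objective 2 frame the comparison per ear, adjusted for handedness, but do not say whether the ears go into separate models or one. Section 10.1 states "Thus a total of 504 subjects need to complete the study", that is, 252 per arm.

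**The concern.** Seven changes from one ear are not seven independent observations. A between-subject effect such as treatment should be judged against variation between subjects. A group-by-frequency model with a single pooled residual judges it against variation between individual readings. If a subject's changes move together, this makes the overall treatment difference look more precise than it is, and usually makes the interaction look less precise.

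Positive correlation is plausible, because exposure and use of hearing protection act on the whole ear, but the documents do not report it. The within-subjects wording does not settle the matter: it concerns baseline against final test, which the change score already absorbs. Correlation among the seven change scores remains.

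At stake is the error rate of one of the two primary efficacy measures. So is the chance of finding a small effect confined to the region near 4 kHz, where Section 2.1 places the typical notch.

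**Working it through.** **Plan's own figure.** There is none for this analysis. The only design figure, 252 per arm, belongs to the STS comparison and is used here only as the number of completers. Using 300 per arm does not change the compound-symmetry error rates.

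**Inputs from the documents.** K = 7 frequencies (5.5.3, 10.2); n = 252 completers per arm (10.1); alpha = 0.05 (10.1), taken as two-sided.

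**Assumptions.** One ear; correlation rho between changes at different frequencies, shown over a range; SDs as stated below.

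**Degrees of freedom.** 504 x 7 = 3,528 values per ear. Less 14 cell means, this leaves 3,514 error df. The between-subject error for group has 504 - 2 = 502.

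**Expected mean squares against the pooled residual** (compound symmetry, equal SDs):
- Group: 1 + (K - 1)rho = 1 + 6rho, so the variance of the overall difference is understated by this factor.
- Group x frequency: 1 - rho, so the error is overstated by 1/(1 - rho).

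Actual size of the nominal 5% group test = 2[1 - Phi(1.96/sqrt(1 + 6rho))]. At rho = 0.3, 1 + 6 x 0.3 = 2.8, 1.96/sqrt(2.8) = 1.171, and the size is 0.241. The relative width of the 95% interval is 1/sqrt(1 + 6rho). Simulated columns use 10,000 null runs.

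| rho | Group, formula | Group, simulated | Interaction, simulated | Interval width vs correct | Coverage |
|---|---|---|---|---|---|
| -0.05 | 1.9% | 1.9% | 6.4% | 120% | 98% |
| 0 | 5.0% | 4.8% | 4.7% | 100% | 95% |
| 0.1 | 12.1% | 11.4% | 2.9% | 79% | 88% |
| 0.3 | 24.1% | 23.7% | 0.6% | 60% | 76% |
| 0.5 | 32.7% | 32.9% | 0.04% | 50% | 67% |

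**Other correlation patterns and unequal SDs.** These rates come from the exact null distribution (1 million draws). The unequal SDs are assumed: 4, 4, 4, 6, 7, 9, 10 dB.

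| Setting | Group | Interaction |
|---|---|---|
| Equal SDs, AR(1) 0.1 / 0.3 / 0.5 / 0.7 | 7.2 / 13.1 / 20.9 / 30.4% | 4.4 / 3.4 / 2.4 / 1.0% |
| Unequal SDs, AR(1) 0.1 / 0.3 / 0.5 | 7.05 / 12.4 / 19.5% | 6.6 / 5.3 / 4.0% |
| Unequal SDs, compound symmetry 0.1 / 0.3 / 0.5 | 11.2 / 22.0 / 30.1% | 5.3 / 2.3 / 0.65% |

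The group test is anti-conservative in every positive-correlation setting. The interaction test is not conservative in all of them. With unequal SDs its numerator has a heavier tail than the reference distribution, which offsets the inflated residual when correlation is weak.

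**Power of the interaction test** (assumed SD 6 dB at every frequency; rho 0 / 0.1 / 0.3 / 0.5):

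| Assumed effect | Pooled residual | Corrected error |
|---|---|---|
| 1.5 dB at 4 kHz only | 45/41/33/23% | 44/49/63/80% |
| 2 dB at 4 kHz only | 75/73/70/66% | 74/80/90/98% |
| 1.5 dB at 3, 4 and 6 kHz | 78/78/77/75% | 78/83/93/99% |
| 3 dB at 4 kHz only | at least 98% | at least 98% |

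**Worst-case illustrations.**
- *Single frequencies, pooled residual.* If SDs rise evenly from 1.0 to 1.6, the mean variance is 1.73. The size is 2[1 - Phi(1.96 x sqrt(1.73)/SD)], which is 1.0% at the lowest SD and 10.7% at the highest, before Newman-Keuls. After Newman-Keuls on the 14 cell means it is at most about 1% at any frequency if frequency means differ by 2 dB or less. The spread of about 1% to 10-11% persists only with assumed 3 dB steps.
- *Both ears pooled as independent readings.* Group error is 17% to 46% (rho 0.1 to 0.5, assumed between-ear correlation 0.3 to 0.7).

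**Check of the remedy** (one ear; equal SDs and SDs 1.0 to 1.6; compound symmetry -0.05 to 0.5; AR(1) 0.5 and 0.7). Between-subject group test 4.5% to 5.6%; Greenhouse-Geisser interaction 4.5% to 5.3%; unstructured interaction 4.7% to 5.5%. The uncorrected repeated-measures interaction gives 7.3% to 8.6% under AR(1), so the sphericity correction is needed too.

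**The case against.** The strongest reply is that the two-by-seven wording describes a factor layout, not an error term. The plan's statisticians use repeated measures ANOVA elsewhere in the section and might well do so here unprompted, in which case the problem disappears. This stands as a limit: the finding is an under-specified model, and a reader who infers that the trial will run at a 24% or 33% error rate goes beyond the documents. It does not remove the point. Naming the method for two analyses and not for the one between them invites the literal reading, and no other section supplies the term.

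Second, objective 2 is about change at the tested frequencies, with an interaction and Newman-Keuls, so the overall group effect is not its sole decision test. That is correct. The largest error rates attach to one of several tests, and the single-frequency inflation mostly vanishes after Newman-Keuls unless frequency means are well separated.

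Third, a reader might infer that positive correlation alone makes the interaction test conservative. It does not: roughly equal SDs or at least moderate correlation are also needed. The power loss also shrinks when the effect spans several frequencies.

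Fourth, pooling both ears as independent goes against the per-ear wording, so the two-ear figures are only a worst case. Finally, the plan does not say its intervals would use the pooled residual; they are too narrow only if they do.

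**Conclusion.** The point holds as a gap in the specification of a primary efficacy analysis. With one pooled residual, the overall group test is invalid whenever changes correlate positively across frequencies. Under compound symmetry with equal SDs, its error rate is more than twice nominal at rho 0.1 and over six times nominal at rho 0.5. This direction survives AR(1) correlation and unequal SDs.

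The interaction result is conditional. The test is conservative, with lost power for small frequency-specific effects, when SDs are similar or correlation is moderate or strong; otherwise it is near nominal or slightly liberal. All sizes rest on assumed correlations and SDs, because the documents give neither, and at zero correlation with equal SDs nothing is wrong.

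The documents do not support a broader reading that the trial's efficacy conclusion as a whole is compromised. The STS comparison by Fisher's exact test uses one outcome per subject, and the sample size was set for STS rates. The point should be fixed before analysis.

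**What to change.** In objective 2, name frequency as a within-subject repeated factor. Test group against between-subject error, and group x frequency with a sphericity correction such as Greenhouse-Geisser. A mixed model with unstructured covariance over frequency is an equivalent choice. Use frequency-specific variances for single-frequency comparisons, and take the promised intervals from the same model.

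State that each ear is analysed separately, as the wording suggests. If the ears are analysed jointly, include ear and group x ear and allow for between-ear correlation. Keep the handedness adjustment. Baseline threshold as a covariate is an optional gain in precision and is not needed for validity.

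The cost is a few sentences in Section 10.2 and a little programming, with no new data and no change of hypothesis. If correlation is positive, the overall group p-value becomes larger and its interval wider, which is the correction. If correlation is near zero, results barely change.

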| STATISTICAL ANALYSIS | 
To confirm that the total daily dose of D-methionine 100mg/kg fractionated into 2 doses of 50 mg/kg each is safe and tolerable.
 
To determine if there is significantly reduced change in threshold hearing in each ear, adjusting for handedness, for the D-methionine group as compared to the placebo group at the tested audiometric frequencies.
 
To determine if there is a significantly lower rate of STS (in either ear) for the D-methionine group compared to the placebo group.
 
To determine if there is a significant difference in reported level of tinnitus between the D-methionine and the placebo groups.
 |

Clinical Trial Schema

List of Abbreviations

| | |
|----------|---|
| AAA | American Academy of Audiology |
| ACE-Mg | ACE-Magnesium |
| ADR | Adverse Drug Reaction |
| AE | Adverse Event/Adverse Experience |
| ANSI | American National Standards Institute |
| CCR | Center for Clinical Research |
| CFR | Code of Federal Regulations |
| COI | Conflict of Interest |
| CONSORT | Consolidated Standards of Reporting Trials |
| CRF | Case Report Form |
| DDEAMC | Dwight D. Eisenhower Army Medical Center |
| D-met | D-methionine |
| DFMO | Difluoromethylornithine |
| DHHS | Department of Health and Human Services |
| DOEHRSHC | Defense Occupational Environmental Health Readiness System-Hearing Conservation |
| DSM | Data and Safety Monitoring |
| FDA | Food and Drug Administration |
| FWA | Federal Wide Assurance |
| GCP | Good Clinical Practice |
| GSH | Glutathione |
| GSSG | Oxidized Glutathione |
| HIPAA | Health Insurance Portability and Accountability Act |
| IB | Investigator's Brochure |
| ICF | Informed Consent Form |
| IDE | Investigational Device Exemption |
| IND | Investigational New Drug |
| IRB | Institutional Review Board |
| ISM | Independent Safety Monitor |
| JC | Joint Commission |
| MACH | Moncrief Army Community Hospital |
| MCRD | Marine Corps Recruit Depot |
| N | Number (typically refers to participants) |
| NAC | N-acetylcysteine |
| NB | Narrow Band |
| NIHL | Noise Induced Hearing Loss |
| NCI | National Cancer Institute, NIH |
| NIH | National Institutes of Health |
| PI | Principal Investigator |
| PK | Pharmacokinetics |
| PTA | Pure Tone Average |
| QA | Quality Assurance |
| QC | Quality Control |
| SAE | Serious Adverse Event |
| SOP | Site Operations Manual |
| STS | Significant Noise-Induced Threshold Shifts |
| WHO | World Health Organization |

Definitions

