4.2 Study Endpoints

4.2.1 Primary Endpoints

- The first primary endpoint is to confirm safety and tolerability of administering up to 100 mg/kg daily, given in divided doses, twice daily (with morning and evening meal). The other primary efficacy endpoint is change from baseline in pure-tone thresholds as measured by absolute change and frequency of significant noise-induced threshold shift (STS).

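### Newman-Keuls, the only correction named for the seven-frequency threshold analysis, does not reliably hold 5% over the D-methionine versus placebo contrasts, and the plan does not say which means it ranks

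*Combined protocol and SAP*

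**What the plan says.** Section 10.2, objective 2, is listed among the primary objectives. It looks for a "significantly reduced change in threshold hearing in each ear, adjusting for handedness" under active treatment relative to placebo, frequency by frequency. The frequencies are listed: "The tested audiometric frequencies will be 0.5, 1, 2, 3, 4, 6 and 8 kHz". The method is "Multi-way (2 groups x 7 frequencies) analysis of variance (ANOVA) with interaction effects", after which "correction for multiple comparisons (Newman-Keuls) will be utilized to determine significance". The Statistical Analysis row of the synopsis repeats the question ("significantly reduced change in threshold hearing in each ear, adjusting for handedness, for the D-methionine group as compared to the placebo group") and adds no correction. Section 4.2.1 makes absolute threshold change one of the two measures of the primary efficacy endpoint, alongside the STS rate.

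The documents do not say which means Newman-Keuls ranks, whether a significant F test must come first, or what familywise level applies to this objective. The 0.05 level appears in section 10.1 ("A power analysis incorporating a 95% confidence level"), where it belongs to the STS sample size. Section 10.2 also plans 95% confidence intervals for all D-methionine versus placebo differences and mentions no adjustment of them.

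**The concern.** The question is D-methionine against placebo at each of seven frequencies: 7 contrasts, or 14 if each ear is tested. Newman-Keuls is a step-down procedure on ranked means. It controls error when all the ranked means are equal, but not when they fall into several separated groups of equal means. A 2 x 7 layout with no drug effect and a noise notch is exactly that: seven pairs of equal means, set apart by frequency. Section 2.1 itself describes a notch near 4 kHz.

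At stake is a frequency-specific claim of protection from a Phase 3 primary analysis. Its false-positive rate and power would depend on the depth of the notch, which is not the drug's doing, and on an unstated choice of which means to rank. Two analysts following the same text could reach different conclusions from the same data.

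**Working it through.** **Inputs from the documents.** 2 arms, 7 frequencies and 2 ears (10.2); alpha 0.05 (10.1, sidedness not stated, two-sided used here); completers per arm 252 (10.1), or 600 x (1 - 0.20)/2 = 240 from the enrolment and attrition figures in the same section.

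**Assumptions, not in the documents.** SD of change 6-8 dB; equal correlation rho between tests, 0 to 0.7; several shapes of mean change over frequency; no drug effect unless stated.

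**Plan's own figure.** The plan gives no error rate for this analysis, so there is none to reproduce. The 252 per arm belongs to the STS test. A pooled two-sided calculation for 38% versus 0.70 x 38% = 26.6% gives 263 rather than 252, but that does not affect what follows, which hardly depends on n.

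**1. Two arm means ranked at each frequency.** The 5% critical value for a range of two means is q(2) = 2.77, and 2.77/sqrt(2) = 1.96. This is an ordinary 0.05 test, so nothing is corrected. Under independence the familywise error is 1 - 0.95^7 = 30.2% for 7 tests and 1 - 0.95^14 = 51.2% for 14. With correlation, by Monte Carlo (400,000 draws):

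| rho | 7 tests | 14 tests (ears separate) |
|---|---|---|
| 0 | 30% | 51% |
| 0.3 | 27% | 44% |
| 0.5 | 23% | 35% |
| 0.7 | 18% | 25% |

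**2. All 14 cell means ranked.** There are 14 x 13/2 = 91 pairs, of which 7 are of interest and 84 compare different frequencies. If all means are equal, a pair must in effect pass q(14) = 4.75, a pairwise p of about 0.00079. The bound is 7 x 0.00079 = 0.55%. Once frequencies separate, the two arms at one frequency become neighbours and are tested at q(2), as in step 1.

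Simulation at n = 252, with frequency means equally spaced in units of the standard error of a cell mean (SD/sqrt(252), so 0.38 dB for SD 6 and 0.50 dB for SD 8), over rho 0 to 0.7:

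- spacing 0: 0.4-0.6%
- spacing 1: 1.9-3.6%
- spacing 3: 13-22%
- spacing 6 or more: 17-31%

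Simulation at 240 per arm, in dB:

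| Mean change over frequency | Chance of at least one false frequency |
|---|---|
| Flat | 0.4-0.8% |
| 0-3 dB notch | about 3-7% (1.3-6.1% in one set of runs) |
| 0-7 dB notch, SD 6 | 10-22% |
| 0-7 dB notch, SD 8 | 7-15% |
| Steps of 3 dB (6 x 3 = 18 dB overall) | 17-30% |

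**3. Direction.** Counting only false findings in favour of D-methionine, the 7-test figures in step 1 become 16%, 14%, 12% and 9% for rho 0, 0.3, 0.5 and 0.7.

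**4. Adjusting over the arm contrasts only.** For 7 contrasts the first Holm threshold is 0.05/7 = 0.0071. With no drug effect Holm has the same familywise error as Bonferroni: 1 - (1 - 0.0071)^7 = 4.9% under independence, 4.1% at rho 0.5 and 3.2% at rho 0.7. For 14 contrasts the threshold is 0.05/14 = 0.0036, with simulated error 2.7-4.9%.

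**5. Power per frequency** for a true 2 dB effect at 3, 4 and 6 kHz, Newman-Keuls on 14 means against Holm on 7 contrasts:

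| Notch | SD 6 | SD 8 |
|---|---|---|
| 0-3 dB | 73% vs 84% | 39% vs 56% |
| 0-7 dB | 88% vs 86% | 55% vs 54% |

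**The case against.** The strongest reply is that section 10.2 describes one 2 x 7 ANOVA with interaction, so Newman-Keuls would naturally be run on all 14 means, and there a shallow notch leaves the error near or below 5%. That is right as far as it goes. A reader might infer that Newman-Keuls gives no protection at all. That is true only if it is run on two means per frequency, and the text does not settle which reading is meant. What remains is that on the 14-mean reading control is lost as the notch deepens.

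A reader might also take 30% as the false-positive rate. It requires uncorrelated frequencies, although all seven are measured in the same ears, and it also requires either the per-frequency reading or widely spaced frequency means. Steps of 3 dB with no two frequencies alike do not resemble a notch near 4 kHz.

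A significant F test as a first step would help. Requiring a valid group or interaction F test would bring the error with no drug effect anywhere down to about 6-9%. The plan states no such requirement. If one frequency were truly protected, the gate would open and the six null frequencies would still carry 16-27% (rho 0.7 to 0) under uncorrected testing.

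The objective is worded as a reduction, so false claims of protection arise at about half the two-sided rates. This stands. At half, the per-frequency reading still gives about 9-14% for rho 0.7-0.3, and the 0-7 dB notch about 3.5-11%.

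Finally, a reader might conclude that the frequency results would be uninterpretable. The planned confidence intervals speak against that: effects would be shown with their precision, and a reader could adjust over the contrasts. The sample size also rests on the STS rate, and that test is unaffected.

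**Conclusion.** The method is wrong as written for the question it serves. On the per-frequency reading it makes no correction: about 18-27% two-sided familywise error for rho 0.7-0.3, and 25-44% if ears are tested separately. On the 14-mean reading it is far too strict when the frequency means are flat (under 1%), about right for a 0-3 dB notch (roughly 3-7%), and too lenient for a 0-7 dB notch (roughly 7-22%). It approaches the uncorrected rates only when frequencies are widely spaced. False benefit is about half of each figure.

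The sizes rest on assumed SD (6-8 dB), correlation, notch shape and completers per arm. The loss of reliable control rests on none of these in particular: it follows from the procedure and from the plan's silence about which means are ranked.

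**What to change.** In section 10.2, objective 2, replace Newman-Keuls with Holm's adjustment, or a permutation max-t that permutes subjects, over the D-methionine minus placebo contrasts only. Make no comparisons between frequencies. Fix the family before unblinding:

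- 14 ear-by-frequency contrasts, because the objective asks about each ear (smallest p below 0.05/14 = 0.0036); or
- 7 contrasts if both ears are combined in one model (smallest p below 0.05/7 = 0.0071).

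The text should name one of these.

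The change takes one sentence and no new data. The cost is a stricter threshold for the smallest p-value than an uncorrected test, with little or no power gain over Newman-Keuls when the notch is deep; the gain comes with a shallow notch. The change controls error within objective 2 only. The Fisher test of STS in objective 3 remains a second primary efficacy test, and multiplicity between the two objectives needs its own rule.

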In order to be a Drill Sergeant Instructor, the Soldier must have achieved a rank of E5 (Sergeant) or higher, which generally takes between 4 to 5 years to obtain. Soldiers in DSS training are generally male (87%), between 21 – 45 years of age and racially diverse. In addition, Soldiers are routinely excluded from participation in DSS training if they have any driving under the influence convictions; domestic violence accusations or if they are under any Uniform Code of Military Justice (UCMJ) action or have any felony convictions. Soldiers are routinely screened for drug use by urinalysis and are excluded if test results are positive. They are also excluded if they fail to pass the Physical Training (PT) test, are restricted from any PT activity, or fail to meet weight, height or pregnancy restrictions.

4.4 Inclusion Criteria:

1. Male or female
2. 21 to 45 years of age
3. Negative pregnancy test confirmed by urine sample at enrollment and prior to taking first study drug dose.
4. Willing to use an effective method of birth control during the study (Female participants should avoid pregnancy and male participants should avoid fathering children during study). *Subject should either abstain from sexual relations or practice a method of birth control while taking part in the study. Except for surgical removal of the uterus, birth control methods such as condoms, a diaphragm or cervical cap, birth control pills, IUD, or sperm killing products are not totally effective in preventing pregnancy. Male study participants should refrain from fathering babies while enrolled in this study.*
5. Pure tone air conduction threshold average at 0.5, 1 and 2 kHz of no greater than 40 dB HL bilaterally with no air bone gaps greater than 10 dB and normal otoscopy and tympanometry screens.
6. Willing to limit the use of nutritional supplements containing or derived from protein to 50 grams of protein per day while participating in this study.
7. Ability to comply with all study requirements

4.5 Exclusion Criteria:

Most of these exclusion criteria apply to DSS candidates, but also apply in this study:

1. History of allergic or idiosyncratic reaction to methionine, amino acid mixtures, nutritional supplements, egg white or other proteins or food additives
2. Vegetarian (Individual excludes meat and fish from their diet)
3. History of chronic balance disorders

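### The threshold-change analysis uses baseline only by subtraction, and does not say how ear or the promised handedness adjustment enters the model

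*Combined protocol and SAP*

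**What the plan says.** Section 4.2.1 makes change in pure-tone threshold part of the primary efficacy endpoint, both as absolute change and as the frequency of significant threshold shift (STS). Objective 2 of section 10.2 covers the absolute change. Its aim is a smaller change on D-methionine "in each ear, adjusting for handedness", and the Statistical Analysis row of the synopsis repeats that aim. The method is a "Multi-way (2 groups x 7 frequencies) analysis of variance (ANOVA) with interaction effects", followed by a Newman-Keuls correction. On baseline it says "Subjects serve as their own controls for audiometric change, which is computed relative to baseline measures".

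Section 5.5.3 tests seven frequencies at baseline and after treatment, and section 9.3 stores the results for each ear. Entry under section 4.4 requires a "Pure tone air conduction threshold average at 0.5, 1 and 2 kHz of no greater than 40 dB HL bilaterally". No section names the baseline threshold as a covariate. Handedness appears only in the synopsis and in section 10.2; it is not in the screening list (section 5.3) or the schedule (section 12.0).

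**The concern.** There are two separate issues.

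The first is precision. Subtracting baseline fixes the slope of follow-up on baseline at 1. When the true slope is below 1, subtraction over-corrects, and a chance baseline difference between arms leaks into the treatment estimate. The entry rules leave room for baseline to vary. The 40 dB HL limit applies to the 0.5, 1 and 2 kHz average, and there is no absolute limit at 3, 4, 6 or 8 kHz, although section 2.1 places the noise notch near 4 kHz.

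The second is specification. The aim contains an adjustment that the named model does not show. An analyst could fit one model per ear, pool the ears or average them. Handedness could enter as a main effect or through an interaction with ear. These choices affect half of the primary efficacy endpoint and should not be made after the data are seen.

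**Working it through.** **The plan's own figure.** The only sample size, in section 10.1, is for the STS rate: 252 per arm, assuming "the rate of significant threshold shift (STS) will be approximately 38% for the control (placebo) group" and a 30% difference. Read as a relative reduction, that is 38% against 0.7 × 38% = 26.6%. The pooled two-sided formula at 0.05 and 80% power gives

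n = [1.96 √(2 × 0.323 × 0.677) + 0.842 √(0.38 × 0.62 + 0.266 × 0.734)]² / 0.114² ≈ 263 per arm.

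So 252 is not reproduced exactly; power at 252 is 78.3%. This has no bearing on the present point, because the plan states no power, SD or correlation for threshold change.

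**Variance per subject, for one ear and frequency.** Let s0 and s1 be the SDs at baseline and follow-up, and r their correlation.

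- Change score: s0² + s1² − 2 r s0 s1
- Baseline-adjusted: s1² (1 − r²)
- Difference: s0² − 2 r s0 s1 + r² s1² = (s0 − r s1)², which is never negative

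In large samples adjustment therefore never does worse. The two are equal only when the slope r s1/s0 is 1. With equal SDs the ratio is (1 − r²) / [2(1 − r)] = (1 + r)/2.

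**Size, over assumed r.** The SE reduction is 1 − √[(1+r)/2]. The last column takes a comparison that has 80% power on raw change and evaluates Φ(2.802/√ratio − 1.96). It is an illustration, not a statement about this trial's power.

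| Assumed r | Variance ratio | SE reduction | 80% power becomes |
|---|---|---|---|
| 0.95 | 0.975 | 1.3% | 81.0% |
| 0.9 | 0.95 | 2.5% | 82.0% |
| 0.8 | 0.90 | 5.1% | 84.0% |
| 0.7 | 0.85 | 7.8% | 86.0% |
| 0.5 | 0.75 | 13.4% | 89.9% |

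These figures hold for a single baseline and a single follow-up measure. How far they carry over to a contrast across seven frequencies and two ears depends on correlations that the documents do not give.

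**Aim against model.**

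| Element | In the aim of objective 2 | In the named model |
|---|---|---|
| Group | yes | yes |
| Frequency | yes | yes |
| Ear | each ear | not mentioned |
| Handedness | adjusted for | not mentioned |
| Baseline threshold | through change | by subtraction only |

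Section 10.2 names repeated-measures ANOVA for side effects and for tinnitus but not for objective 2. How the 14 thresholds per subject (7 frequencies × 2 ears) are treated as correlated is therefore also unstated.

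**The case against.** The endpoint is defined as change from baseline, so analysing change follows the protocol. Assignment is random and 1:1 (section 5.4), so regression to the mean is expected equally in both arms, and chance imbalance adds variance rather than systematic bias. All of this stands. A reader might infer that the raw-change comparison is biased or invalid; the design does not support that.

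A reader might also infer that the handedness adjustment will be left out. The documents do not show this. The synopsis and section 10.2 both commit to it, and a parenthesis describing the layout does not rule out further covariates. Nor is a missing ear factor an error in itself, since one model per ear fits the stated aim and needs none. What remains is that the text does not say which is meant or how handedness enters.

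It would also go too far to say that handedness is not collected. The change log for version 4.1 shows that the case report forms became separate documents, and they are not available here.

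Finally, the gain may be small. Audiometric thresholds may correlate highly over a few weeks, and at r = 0.9 the SE falls by only 2.5%. If noise exposure widens the follow-up SD, the slope moves towards 1 and the gain shrinks further. The entry limit shows that baseline may vary, not how much it does.

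**Conclusion.** The point holds as one of efficiency and specification, not of validity. Using baseline only by subtraction gives up precision that data already collected would supply: about 1.3% to 13% of the SE for r from 0.95 to 0.5, assuming equal SDs and one measure at each visit. Since r is unknown, no single figure can be defended. The STS sample size is unaffected.

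The firmer finding rests on the text alone: objective 2 promises a per-ear, handedness-adjusted comparison, and the named layout neither shows a handedness term nor says how the two ears are handled. The aim and the model should be reconciled before unblinding.

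**What to change.** State one model for objective 2. Analyse threshold change (or post-training threshold) in a repeated-measures mixed model with:

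- treatment, frequency and treatment × frequency;
- the baseline threshold at the same ear and frequency;
- ear, or a separate model for each ear;
- handedness, with ear × handedness if the ears are modelled together;
- a subject random effect.

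With baseline in the model, change and post-training threshold give the same treatment estimate, so the endpoint need not be redefined. If the ears are modelled separately, say how the two results are combined into a conclusion. Confirm that handedness is recorded at baseline, and add it if it is not.

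The cost is SAP wording and, at most, one form field. No new test or visit is needed.
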